7.9.6 Reporting of Adverse Events and Serious Adverse Events

Patients will be monitored for all AEs from the time the first dose of study treatment is administered through 30 days after the last dose of study treatment and 90 days after the last dose of pembrolizumab. All AEs/SAEs occurring through the reporting period (30 days after last dose of danvatirsen or 90 days after last dose of pembrolizumab, whichever is longer) or until the time the patient begins a new anticancer treatment are reported in the CRF irrespective of causality. All AEs and SAEs that occur from the signing of the ICF until the first dose of study treatment should be recorded in the eCRF only if the event was related to a study procedure.

All patients with treatment-related AEs/SAEs should be observed until resolution or stabilization of the event. Any SAE occurring after the reporting period must be promptly reported if a causal relationship to the study treatment(s) is suspected.

Elective or previously scheduled hospitalizations for pre-existing conditions that have not worsened after initiation of treatment should not be classified as SAEs. For example, an admission for a previously scheduled ventral hernia repair would not be classified as an SAE.

All AEs should be recorded individually unless, in the opinion of the Investigator, the AEs constitute components of a recognized condition, disease, or syndrome. In the latter case, the condition, disease, or syndrome should be reported rather than each individual sign or symptom. If a constellation of signs and/or symptoms cannot be medically characterized as a single diagnosis or syndrome at the time of reporting, each individual event should be recorded as an AE or SAE, as appropriate, on the relevant form(s) (SAE Report Form and/or AE form). If a diagnosis is subsequently established, it should be reported as follow-up information becomes available. If a diagnosis is determined after the reporting of the constellation of symptoms, the signs/symptoms should be updated to reflect the diagnosis.

In general, disease progression should not be reported as an AE (or an SAE) or cause of death in this study. Instead, the AEs (or SAEs) considered as complications of disease progression should be reported. However, if no specific complications of disease progression can be identified that explain the clinical observations, “disease progression” may be reported as an SAE or cause of death.

Each AE will be evaluated for duration, severity according to the CTCAE v5.0, seriousness, and causal relationship to each study treatment. The action taken with each study treatment and the outcome must also be recorded.

All SAEs, regardless of relationship to each study treatment, must be reported immediately (within 24 hours of awareness of event by Investigator) to the Sponsor and contract research organization (CRO) pharmacovigilance group. All SAE notifications should be made by completing the AE eCRF in the electronic data capture (EDC) system. Follow-up SAE reports must be submitted by the Investigator as new information becomes available.

The Medical Monitor for this study may be contacted for advice or assistance. Contact details will be provided separately in a study contact list.

7.9.7 Regulatory Aspects of Adverse Event Reporting

The Sponsor and/or sponsor's designee is responsible for submitting reports of SAEs associated with the use of the study treatments to the appropriate regulatory authority (e.g., the US FDA), Investigators, and central IRB/EC in accordance with all applicable regulations and guidelines.

It is the responsibility of the Investigator to notify their local IRB of SAEs that occur at his or her site per IRB requirements. Investigators will be notified of all suspected unexpected serious adverse reactions (SUSARs, i.e., via 7-/15-Day Safety Reports) that occur during any clinical studies of danvatirsen. Each site is responsible for notifying their local IRB of these additional SUSARs in accordance with local regulations.

7.9.8 Pregnancy

Any pregnancy must be reported to the Sponsor or designee within 24 hours of the Investigator's knowledge of the pregnancy using a Pregnancy Report Form.

Pregnancy is not considered an AE unless there is cause to believe that the study treatments may have interfered with the effectiveness of a contraceptive medication or if the outcome of the pregnancy meets SAE criteria (miscarriage or congenital anomaly/birth defect, etc.), in which case it should be reported in the same manner and timelines as an SAE. In addition, any infant death or congenital anomaly that the Investigator suspects is related to in utero exposure to the study treatments should also be reported as an SAE. Hospitalization for normal delivery of a healthy newborn is not an SAE.

Pregnancies occurring in patients during the study treatment period and until 30 days after the patient's last dose of study treatments are considered immediately reportable events. If a pregnancy occurs in a patient, study treatments must be discontinued immediately. The pregnant woman should be referred to an obstetrician/gynecologist experienced in reproductive toxicity for further evaluation and counseling. The Investigator will observe the pregnant woman until completion of the pregnancy and must notify the Sponsor of the outcome within 24 hours of the Investigator's knowledge of the pregnancy outcome. This notification includes pregnancies resulting in live, "normal" births.

If a male patient impregnates his female partner, the study personnel at the site should be informed immediately and the pregnancy reported to the Sponsor.

7.9.9 Overdose

For danvatirsen and/or pembrolizumab, administration of doses significantly exceeding those specified in the protocol (>10% above the specified dose) may be considered to be an overdose. In all cases, Investigators should be advised that any patient who receives a higher dose than that intended should be monitored closely, managed with appropriate supportive care, and followed up expectantly. There is currently no specific treatment in the event of an overdose of study drugs. All overdoses or medication errors should be reported to the Sponsor within 24 hours.

An overdose with associated AEs is recorded as the AE diagnosis/symptoms on the relevant AE modules in the eCRF.

7.10 Pharmacokinetic Assessments

Venous blood samples for determination of danvatirsen concentrations in plasma will be taken at the times presented in [Table 7](#). All patients in the danvatirsen + pembrolizumab arm will have sparse PK samples collected at Cycle 2 Day 1, Cycle 5 Day 1, and EOT. For 10 US patients in the danvatirsen + pembrolizumab arm who are participating in the intense PK subset, additional samples will be collected at Cycle 1 Day 1 and Cycle 1 Day 5. The date and time of collection of each sample will be recorded.

PK parameters will be determined for danvatirsen. Possible relationships between PK and pharmacodynamic variables, efficacy, and/or selected toxicities will be explored, as appropriate.

Blood samples should be collected from the arm opposite from the investigational drug infusion, or from another site if collected within 24 hours of dosing.

Retained/residual PK samples may also be used to evaluate safety or efficacy aspects related to concerns arising during or after the study. This includes their use in the development and/or validation of bioassays.

Please refer to the Laboratory Manual for details on collection and processing of blood PK samples.

7.11 Immunogenicity Assessments

Venous blood samples for the assessment of ADA levels will be drawn at the timepoints presented in [Table 8](#) from patients receiving danvatirsen + pembrolizumab. The date and time of collection of each sample will be recorded.

Blood samples should be collected from the arm opposite from the investigational drug infusion, or from another site if collected within 24 hours of dosing.

Retained/residual ADA samples may also be used to evaluate safety or efficacy aspects related to concerns arising during or after the study. This includes their use in the development and/or validation of bioassays.

Please refer to the Laboratory Manual for details on collection and processing of blood ADA samples.

7.12 Pharmacodynamic and Biomarker Assessments

Whole blood samples and tissue specimens are to be collected according to the SoA ([Section 8.1](#)).

7.12.1 Tissue Samples

An FFPE archival or fresh tumor sample collected during screening is required prior to randomization.

- Tissue samples will be used to assess pharmacodynamic activity of danvatirsen and exploratory biomarker assessments.
- Tumor tissue from a fresh biopsy (in FFPE) is preferred at screening if safe/feasible to obtain and consented to by the patient. If surgical resection of an accessible tumor is possible, then in addition to a piece of the tumor going to FFPE, 2 frozen pieces of the resection biopsy should be taken (1 each for RNA and protein analysis).
- If a fresh biopsy is not safe/feasible or not consented to by the patient, an archival sample may be provided.
 - If an archival sample is provided, it should be from the most recent biopsy of a tumor lesion within the previous 24 months collected either at the time of or after the diagnosis of advanced or metastatic disease and from a site not previously irradiated. Approximately 10 to 20 slides of freshly prepared unstained 5-micron sections from the tumor block must be provided.

For US patients only that consented to the optional tissue study, additional fresh tumor samples are requested as soon as possible after Cycle 2 Day 1 (i.e., after study treatment has been administered) and at EOT, if safe/feasible to obtain. These tumor samples will be used to further define the tissue/plasma ratio of danvatirsen and evaluate the effects of danvatirsen on the levels of STAT3 expression (RNA and/or protein) and potentially other gene expression in STAT and related pathways.

Tissue samples will be sent to a central laboratory or another facility approved by the Sponsor for analysis and storage.

See the study Laboratory Manual for further guidance on tissue collection requirements and instructions.

7.12.2 Biomarker Blood Samples

Whole blood samples will be collected for evaluation of exploratory biomarkers. The following samples for biomarker research are required:

- **Whole blood samples (All patients):** Whole blood will be collected at the timepoints specified in [Table 8](#) to evaluate the effects of danvatirsen on the level of STAT3 expression and other gene expression.
- **Whole blood samples for isolation of peripheral blood mononuclear cells (PBMCs) (US only):** Whole blood will be collected at the timepoints specified in [Table 8](#) to evaluate the effects of danvatirsen on the level of STAT3 expression and potentially other gene expression in PBMCs.
- **Whole blood samples for serum (US only) and plasma biomarkers (All patients):** Whole blood will be collected at the timepoints specified in [Table 8](#) to evaluate the effects of danvatirsen on the level of circulating cytokines and other proteins.

Samples for exploratory biomarkers will be sent to a central laboratory or another facility approved by the Sponsor for storage and analysis. See the study Laboratory Manual for further guidance on blood sample collection requirements and instructions.

7.12.3 Storage and Destruction of Biological Samples

Biological samples used for PK, pharmacodynamic, ADA, and biomarker analysis may be retained at a central laboratory or another facility approved by the Sponsor until research and development of danvatirsen is completed, after which the samples will be destroyed.

Residual unused samples may be retained at a central laboratory or another facility approved by the Sponsor indefinitely as they may be used to support further bioassay or biomarker development for danvatirsen. Samples will be destroyed after use or at such time they are not needed for further research.

Flamingo Therapeutics

Activity and Safety of Danvatirsen and Pembrolizumab in HNSCC

8 May 2025

Trial ID: FLM-6774-201

Amendment 4

8 ASSESSMENTS AND PROCEDURES BY STUDY VISIT

The timing of the study assessments and procedures are summarized in the Schedule of Activities ([Table 6](#)).

8.1 Schedule of Activities

Table 6: Schedule of Activities

Assessments	Screening	Cycle 1				Cycle 2			Cycle 3 & Cycle 4			Cycle 5 and Subsequent Cycles			Cycle 5 and Subsequent Cycles			EOT ^a (+7D)	Safety Follow-up ^b 30D (+7D)	Safety Follow-up ^b 90D (+7D)	Survival Follow-up Q12W (±7D)
		-28 to 0	D1	D3 ^c & D5 ^c + - 1D	D8 ± 3D	D15 ±3D	D1 ± 3D	D8 ± 3D	D15 ± 3D	D1 ± 3D	D8 ± 3D	D15 ± 3D	D1 ±3D	D8 ±3D	D15 ±3D	D1 ±3D	D8 ±3D ^c	D15 ±3D ^c			
Informed consent ^c	X																				
Demography; baseline characteristics; medical, surgical, and cancer history	X																				
Tumor tissue collection ^d	X					X													X		
Randomization following final confirmation of eligibility ^e		X																			
Complete physical examination ^f	X	X				X			X			X			X			X			
Targeted physical examination ^f			X	X		X	X		X	X		X	X		X	X			X		
ECOG performance status	X	X				X			X			X			X			X	X		
Vital signs ^g	X	X	X	X	X	X	X	X	X	X	X	X	X	X	X	X		X	X		
Height	X																				
Weight ^f	X					X			X			X			X			X	X		
12-Lead ECG in triplicate	X																		X		

Assessments	Screening	Cycle 1				Cycle 2			Cycle 3 & Cycle 4			Cycle 5 and Subsequent Cycles			Cycle 5 and Subsequent Cycles			EOT ^a (+7D)	Safety Follow-up ^b 30D (+7D)	Safety Follow-up ^b 90D (+7D)	Survival Follow-up Q12W (±7D)
		-28 to 0	D1	D3 ^c & D5 ^c + - 1D	D8 ± 3D	D15 ±3D	D1 ± 3D	D8 ± 3D	D15 ± 3D	D1 ± 3D	D8 ± 3D	D15 ± 3D	D1 ±3D	D8 ±3D	D15 ±3D	D1 ±3D	D8 ±3D ^c	D15 ±3D ^c			
Laboratory safety tests (hematology) ^f	X	X		X	X	X	X	X	X	X	X	X	X	X	X	X		X	X		
Laboratory safety tests (serum chemistry) ^f	X	X		X	X	X	X	X	X	X	X	X	X			X		X	X		
Laboratory safety tests (coagulation) ^f	X	X				X			X			X			X			X	X		
Urinalysis ^f	X	X				X			X			X			X			X	X		
Thyroid function tests ^f	X	X				X			X			X			X			X	X		
Pregnancy test ^h	X	X				X			X			X			X			X	X	X	
Concomitant medications ⁱ	X	X		X	X	X	X	X	X	X	X	X	X	X	X ^s	X ^s	X	X			
AE ⁱ	X	X		X	X	X	X	X	X	X	X	X	X	X	X ^s	X ^s	X	X	X	X	
Tumor assessments ^j	X								X			X			X			X			
Danvatirsen ^k		X	X	X	X	X	X	X	X	X	X	X	X	X							
Pembrolizumab ^l		X				X			X			X			X						
Sparse Pharmacokinetics ^m						X						X						X			
Intense Pharmacokinetics ^m		X	X																		
ADA ⁿ		X				X						X						X			
US patients only whole blood, serum, and plasma biomarkers ^o		X		X	X	X			X			X			X			X			

Assessments	Screening	Cycle 1				Cycle 2			Cycle 3 & Cycle 4			Cycle 5 and Subsequent Cycles			Cycle 5 and Subsequent Cycles			EOT ^a (+7D)	Safety Follow-up ^b 30D (+7D)	Safety Follow-up ^b 90D (+7D)	Survival Follow-up Q12W (±7D)
		-28 to 0	D1	D3 ^c & D5 + - 1D	D8 ± 3D	D15 ±3D	D1 ± 3D	D8 ± 3D	D15 ± 3D	D1 ± 3D	D8 ± 3D	D15 ± 3D	D1 ±3D	D8 ±3D	D15 ±3D	D1 ±3D	D8 ±3D ^c	D15 ±3D ^c			
ROW patients only whole blood and plasma biomarkers ^d		X				X							X			X			X		
US patients only PBMC biomarkers ^e		X		X	X	X			X				X			X			X		
Survival status and anticancer therapy																			X	X	X

Abbreviations: ADA = anti-drug antibody; AE = adverse event; C = cycle; D = day; ECG = electrocardiogram; ECOG = Eastern Cooperative Oncology Group; EOT = end of treatment; ICF = informed consent form; IRT = Interactive Response Technology; PBMC = peripheral blood mononuclear cell; PD = progressive disease; PK = pharmacokinetic; Q3W = every 3 weeks; Q12W = every 12 weeks; SAE = serious adverse event

- a. EOT assessments need not be repeated if performed within the previous 14 days (or 30 days for imaging). When the last study visit is the same as the EOT visit, default to the EOT and consider any additional procedures unscheduled.
- b. The 30-day safety follow-up visit will occur 30 days (+7 days) after the last dose of study treatment or prior to the start of new anticancer therapy, whichever occurs first. The 90-day safety follow-up may be a telephone communication or clinic visit, at the Investigator's discretion, and will occur 90 days (+7 days) after the last dose of pembrolizumab or before initiation of new anticancer therapy, whichever occurs first.
- c. Informed consent may be obtained any time prior to screening procedures. There is no defined visit window between the date of ICF and C1D1.
- d. Fresh tumor biopsies are requested if safe/feasible at baseline before treatment, and for US patients that consented to the optional tissue study as soon after C2D1 treatment as possible, and at EOT, but this is not a requirement. If a fresh biopsy is not safe/feasible or not consented to by the patient, an archival sample must be provided during screening.
- e. Randomization via the IRT may be performed prior to C1D1 to allow for scheduling and study treatment preparation.
- f. To facilitate scheduling of predose assessments, a window of -2 days is allowed to obtain the following procedures prior to dosing a patient: physical examination, weight, laboratory safety tests (hematology, serum chemistry, and coagulation), urinalysis, and thyroid function tests.
- g. Vital signs include temperature, pulse, respiratory rate, blood pressure, and oxygen saturation.
- h. For female patients of childbearing potential, serum or urine. The pregnancy test at the 90 day safety follow up visit is required for all patients in the UK and as clinically indicated for all other patients.
- i. Patients are to be followed up for 30 days (+7 days) after the last dose of study treatment for any new reports of AEs, SAEs, and concomitant medications. Tracking of AEs will continue for all patients treated with pembrolizumab for 90 days (±7 days) after the last dose of pembrolizumab or until the initiation of subsequent anticancer therapy.

Flamingo Therapeutics
Activity and Safety of Danvatirsen and Pembrolizumab in HNSCC
8 May 2025

Trial ID: FLM-6774-201
Amendment 4

- j. Tumor assessments performed within 30 days of C1D1 may be used as the baseline tumor assessments. Tumor assessments will be performed every 6 weeks until tumor progression. Patients who discontinue treatment for reasons other than PD will continue to undergo tumor assessments every 6 weeks until PD or the initiation of new anticancer therapy. To facilitate scheduling of tumor assessments, a window of ± 7 days is allowed.
- k. For C1 Week 1, danvatirsen will be administered on D1, D3, and D5 as a loading dose period. Starting with C1 Week 2, danvatirsen will be administered every week on D1, D8, and D15 of each treatment cycle; doses will have a ± 2 -day dosing window.
- l. For pembrolizumab, a window of ± 7 days is allowed for dosing days. Patients will receive pembrolizumab Q3W on D1 of each cycle.
- m. For C1 Week 1, intense PK sampling will be performed on D1 and D5 for 10 US patients in the danvatirsen + pembrolizumab arm. Sparse PK sampling also occurs on C2D1, C5D1 and EOT for all patients in the danvatirsen + pembrolizumab arm. Detailed PK sampling times are provided in [Table 7](#).
- n. ADA will be assessed for danvatirsen + pembrolizumab patients at C1D1, C2D1, C5D1, and EOT, as shown in [Table 8](#).
- o. Whole blood will be collected for the assessment of whole blood, serum, and plasma biomarkers in all US patients at C1D1, D8, and D15; C2D1; C3D1; C5D1; and EOT, as shown in [Table 8](#).
- p. Whole blood will be collected for the assessment of whole blood and plasma biomarkers in all ROW patients at C1D1; C2D1; C5D1; and EOT, as shown in [Table 8](#).
- q. Whole blood will be collected for assessment of PBMC biomarkers in all US patients at C1D1, D8, and D15; C2D1; C3D1; C5D1; and EOT, as shown in [Table 8](#).
- r. C1D3 and C1D5 visits are only applicable to patients on the danvatirsen + pembrolizumab arm. A minimum of one day is required between the D1, D3 and D5 danvatirsen doses. Note: The visit windows on D1, D3 and D5 do not apply to patients that are participating in the intense PK subset.
- s. D8 and D15 AE and concomitant medication assessments for patients on the pembrolizumab arm, may be conducted via a phone call beginning with Cycle 5. In person visits should occur as clinically indicated.

8.2 Pharmacokinetic, Immunogenicity, and Biomarker Sampling

Table 7: Pharmacokinetic Sampling

Timepoint		PK Sample	
Cycle	Day	10 Danvatirsen + Pembrolizumab US Patients	All Other Danvatirsen + Pembrolizumab Patients
1	1	Predose and at 0.5 h (± 5 min), 1 h (end of infusion; ± 10 min), 2 h (± 15 min), 4 h (± 30 min), and 6 h (± 30 min) after the start of the danvatirsen infusion	
1	5	Predose and at 0.5 h (± 5 min), 1 h (end of infusion; ± 10 min), 2 h (± 15 min), 4 h (± 30 min), and 6 h (± 30 min) after the start of the danvatirsen infusion	
2	1	Predose and 2 h (± 15 min) after the start of the danvatirsen infusion	Predose and 2 h (± 15 min) after the start of the danvatirsen infusion
5	1	Predose and 2 h (± 15 min) after the start of the danvatirsen infusion	Predose and 2 h (± 15 min) after the start of the danvatirsen infusion
EOT	EOT	Any time during the EOT visit	Any time during the EOT visit

Abbreviation: PK = pharmacokinetic

Table 8: Immunogenicity and Biomarker Sampling

Timepoint		Immunogenicity Sample	Whole Blood, Serum, and Plasma Biomarker Sample	PBMC Biomarker Sample	Whole Blood and Plasma Biomarker Sample
Cycle	Day	All Danvatirsen + Pembrolizumab Patients	US Patients	US Patients	ROW Patients
1	1	X (Predose)	X (Predose)	X (Predose)	X (Predose)
1	8		X	X	
1	15		X	X	
2	1	X	X	X	X
3	1		X	X	
5	1	X	X	X	X
End of Treatment		X	X	X	X

Abbreviation: PBMC = peripheral blood mononuclear cell

9 STATISTICAL CONSIDERATIONS

A summary of the study design and the planned statistical analyses for the primary and key secondary endpoints is presented below. A more technical and detailed description of the statistical methodology will be documented in the statistical analysis plan (SAP). Changes to the analyses will be described and justified in the CSR for the study.

9.1 Statistical Hypotheses

The primary efficacy evaluation will be the magnitude of ORR in each of the treatment arms and the probability that the combination arm ORR is superior to that of the control (monotherapy) arm, that is $Pr(ORR_{comb} > ORR_{con} | data)$.

9.2 Sample Size

Sample size considerations were based on monitoring the primary efficacy endpoint, ORR, using a 2-arm Bayesian optimal phase 2 (BOP2) design (Zhao et al 2022).

Specifically, let n denote the interim sample size and N denote the maximum sample size. Let ORR_{con} denote the control ORR and ORR_{comb} denote the combination treatment ORR. We define the null hypothesis $H_0: ORR_{comb} \leq ORR_{con}$, under which the combination arm is deemed as unacceptable, respective to the control. We employ the following Bayesian rule to make a go/no-go decision:

(Futility stopping) stop enrolling patients and claim that the experimental arm is unacceptable if:

$$Pr(ORR_{comb} > ORR_{con} | data) < \lambda \left(\frac{n}{N}\right)^\alpha,$$

Where $\lambda=0.96$ and $\alpha=0.94$ are design parameters optimized to maximize the power under $H_0: ORR_{con} = 0.15$ and $ORR_{comb} = 0.43$, while controlling the type I error rate at 0.05 under $ORR_{con} = ORR_{comb} = 0.15$. This optimization is performed assuming a vague prior Beta(0.5,0.5) for ORR_{con} and ORR_{comb} .

An interim futility analysis is planned when ORR can be assessed for the first 39 patients, and the final ORR analysis is planned after 81 patients are followed for a minimum of 3 months (2 radiologic scans). A 2:1 combination:control randomization will be used for the 2 arms and will yield 83% power at the 1-sided 5% alpha based on the above decision rule to reject the null hypothesis and conclude that the combination arm is superior compared to the control:

At the interim analysis: $Pr(ORR_{comb} > ORR_{con} | data) > 0.5$, and

At the final analysis: $Pr(ORR_{comb} > ORR_{con} | data) > 0.96$

The go/no-go criteria, also presented in detail in Table 9 below, are non-binding.

The operating characteristics of the design, based on 100000 simulations using the BOP2 application, are presented in Table 10.

Table 9: Optimized Stopping Boundaries

Control N	Combination N	# CR/PR in Control	Stop for Futility if # of CR/PR in Combination - # of CR/PR in Control ≤
13	26	0	0
13	26	1~2	1
13	26	3	2
13	26	4	3
13	26	5	4
13	26	6	5
13	26	7	6
13	26	8	7
13	26	9	8
13	26	10	9
13	26	11	10
13	26	12	11
13	26	13	12
27	54	0	4
27	54	1	7
27	54	2	10
27	54	3	11
27	54	4	13
27	54	5	15
27	54	6	16
27	54	7	17
27	54	8	18
27	54	9	20
27	54	10	21
27	54	11	22
27	54	12~13	23
27	54	14	24
27	54	15	25
27	54	16~17	26
27	54	18~19	27
27	54	20~26	28
27	54	27	27

Abbreviations: CR = complete response; PR = partial response

Table 10: Operating Characteristics

Scenario	% ORR Control	% ORR Combination	Early Futility Stopping (%)	Claim Promising (%)	Average Sample Size
1	15	15	46.1	4.6	62
2	23	23	43.8	4.5	63
3	20	40	7.1	54.6	78
4	23	43	7.7	52.9	78
5	25	50	4.5	68.6	79
6	15	43	1.9	82.7	80

Abbreviation: ORR = objective response rate

Additional futility monitoring criteria will be taken into consideration for the subgroup of patients with CPS ≥ 1 and < 20 . Specifically, if no more than one patient achieves a response (confirmed or unconfirmed CR or PR within the first two scans) in the first 10 patients enrolled in the combination arm for this subgroup, there will be no further enrollment in this subgroup, and the study will continue to enroll in the CPS ≥ 20 subgroup, consistent with any guidance based on the monitoring criteria outlined in [Table 9](#). Additionally, accrual in the CPS ≥ 1 and < 20 subgroup will pause, if no responses have been achieved, but response data for the first 10 patients in that subgroup are not yet mature, defined as at least 2 scans assessed.

Considering the limited size of the CPS ≥ 1 and < 20 subgroup, the futility criteria were derived based on a single arm BOP2 design with the interim assessment after 10 patients, a final assessment of 27 patients (half of the intended size of the combination arm) testing a null hypothesis of 15% ORR (KEYNOTE-048 pembrolizumab monotherapy ORR for this subgroup ([Burtness et al 2022](#))) vs. an alternative hypothesis of 29% ORR (SCORES combination arm for this subgroup), at 1-sided 10% level with approximately 65% power.

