## 8 INTERIM ANALYSIS

An interim futility analysis is planned for when ORR can be assessed for the first 39 patients. Tumor assessment data for the interim analysis will be restricted to up until the earliest date in which all 39 patients have received at least one dose of study drug. All demographic and safety data reported until the time of the datacut will be included in the report.

The final ORR analysis is planned after 81 patients are followed for a minimum of 3 months (2 radiologic scans). A 2:1 combination: control randomization will be used for the 2 arms and the (Futility stopping) stop enrolling patients and claim that the experimental arm is unacceptable if:

$$Pr(ORR_{comb} > ORR_{con} | data) < \lambda(n/N)\alpha,$$

Where  $\lambda=0.96$  and  $\alpha=0.94$  are design parameters optimized to maximize the power under  $H0$ :  $ORR_{con} = 0.15$  and  $ORR_{comb} = 0.43$ , while controlling the type I error rate at 0.05 under  $ORR_{con} = ORR_{comb} = 0.15$ . This optimization is performed assuming a vague prior Beta(0.5,0.5) for  $ORR_{con}$  and  $ORR_{comb}$ .

Based on the above decision rule, to reject the null hypothesis and conclude that the combination arm is superior compared to the control:

At the interim analysis:  $Pr(ORR_{comb} > ORR_{con} | data) > 0.5$ , and

At the final analysis:  $Pr(ORR_{comb} > ORR_{con} | data) > 0.96$

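### The interim go threshold is written as 0.5, but the plan's own formula and Table 9 use 0.483, and the two give different decisions when observed response rates are equal

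*Protocol*

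**What the plan says.** Protocol 9.2 sets a Bayesian futility rule: "stop enrolling patients and claim that the experimental arm is unacceptable if" the posterior probability that the combination ORR exceeds the control ORR falls below λ(n/N)^α. The constants follow: "Where $\lambda=0.96$ and $\alpha=0.94$ are design parameters optimized to maximize the power". Each arm has a Beta(0.5, 0.5) prior. The looks are fixed at n = 39 ("An interim futility analysis is planned when ORR can be assessed for the first 39 patients") and N = 81 ("the final ORR analysis is planned after 81 patients are followed for a minimum of 3 months"), with 2:1 allocation.

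The same section then restates the rule as two numerical criteria. The interim one requires "ORR_{con} | data) > 0.5" and the final one requires a probability above 0.96. Of these criteria it says: "The go/no-go criteria, also presented in detail in Table 9 below, are non-binding". Table 9 lists the boundaries for 13 control and 26 combination patients at the interim, and for 27 and 54 at the end. Table 10 gives early-stopping rates, the chance of a promising claim and average sample size for six scenarios.

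SAP section 8 repeats the formula, the constants and the prior. Its line beginning "At the interim analysis" carries the same 0.5. It does not reproduce Table 9.

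**The concern.** The text presents the formula, the 0.5 criterion and Table 9 as one rule. Evaluated at the interim sample size, the formula does not give 0.5, so the text conflicts with either the formula or the table. An interim result falling between the two cutoffs would be a no-go by the written criterion and a continue by Table 9.

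The outcomes affected include 2/13 vs 4/26 and 3/13 vs 6/26, which are quite plausible if danvatirsen adds nothing. Someone working from the SAP alone sees the formula and the 0.5 but has no table to settle which applies. If 0.5 were applied, the early-stopping column of Table 10 would no longer describe the trial.

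**Working it through.** **Inputs (Protocol 9.2, repeated in SAP section 8 unless noted).** λ = 0.96; α = 0.94; n = 39; N = 81; Beta(0.5, 0.5) prior in each arm; 13 control and 26 combination patients at the interim, 27 and 54 at the end (Table 9, protocol only).

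**Step 1: the cutoff from the formula.** (39/81)^0.94 = 0.5031, and 0.96 × 0.5031 = 0.4829. If λ and α are themselves rounded to two decimals, the cutoff lies between 0.955 × (39/81)^0.945 = 0.479 and 0.965 × (39/81)^0.935 = 0.487. Rounding of the constants therefore does not reach 0.5. At n = N the formula gives 0.96, which agrees with the written final criterion.

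**Step 2: reproduce Table 9.** For x_c control and x_t combination responders, the posteriors are Beta(0.5 + x_c, 0.5 + 13 − x_c) and Beta(0.5 + x_t, 0.5 + 26 − x_t). The probability that the combination rate is larger was obtained by numerical integration and checked by Monte Carlo on eight cells.

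- A cutoff of 0.4829 reproduces the interim boundary for all 14 possible control counts (0 to 13), and 0.96 reproduces the final boundary for all 28 (0 to 27).
- A cutoff of 0.5 changes the interim boundary for 2, 3, 4, 5 and 6 control responders from a difference of 1, 2, 3, 4, 5 to 2, 3, 4, 5, 6.
- Table 9 itself brackets the cutoff that produced it. With 1 control and 2 combination responders it stops (posterior 0.4732). With 2 and 4 it continues (posterior 0.4844). The cutoff must be above 0.4732 and no higher than 0.4844.

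**Step 3: the outcomes in conflict.**

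| Control (of 13) | Combination (of 26) | Posterior probability | Formula and Table 9 | Written 0.5 |
|---|---|---|---|---|
| 2 | 4 | 0.4844 | continue | not met |
| 3 | 6 | 0.4898 | continue | not met |
| 4 | 8 | 0.4934 | continue | not met |
| 5 | 10 | 0.4963 | continue | not met |
| 6 | 12 | 0.4988 | continue | not met |

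In each, the combination arm has exactly twice as many responders in twice as many patients. In every other outcome the two rules agree.

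**Step 4: reproduce Table 10, then change the cutoff.** Exact two-stage binomial enumeration with the Table 9 final boundary gives these early-stopping rates:

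| ORR control/combination | Table 10 | Exact at 0.483 | Exact at 0.5 | Difference, points |
|---|---|---|---|---|
| 15/15 | 46.1% | 46.44% | 54.78% | 8.34 |
| 23/23 | 43.8% | 44.10% | 54.34% | 10.24 |
| 20/40 | 7.1% | 7.14% | 11.10% | 3.96 |
| 23/43 | 7.7% | 7.79% | 11.79% | 4.00 |
| 25/50 | 4.5% | 4.52% | 6.90% | 2.38 |
| 15/43 | 1.9% | 1.93% | 3.45% | 1.52 |

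The last column is also the probability of landing in one of the five conflicting outcomes. The small gaps between Table 10 and the 0.483 column (at most 0.34 points) are far smaller than the gaps to the 0.5 column.

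**Step 5: the other operating characteristics.** The promising claim at 15/43 is 82.56% under 0.483 (Table 10: 82.7%) and 82.15% under 0.5. At 15/15 it is 4.53% (Table 10: 4.6%) and 4.51%. Across the six scenarios the change is at most 0.47 points (23/43: 52.82% to 52.35%). Average sample size at 15/15 is 61.5 (Table 10: 62) and 58.0.

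**The case against.** The strongest reply is that 0.5 is not a stop rule at all. The only instruction to stop is the formula, which agrees with Table 9. The 0.5 appears among the conditions for concluding superiority, and nothing says outright that missing it ends enrolment. This does not hold up: Protocol 9.2 calls these the go/no-go criteria and says Table 9 presents them, so missing 0.5 is a no-go exactly where Table 9 continues.

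Several other points do stand and limit the weight of the finding:

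- The rule is non-binding, so the sponsor may continue in any case. A non-binding rule still needs one value, or an override cannot be recognised and documented as one.
- The conflict is confined to five outcomes with equal observed rates. The two lowest, 2 vs 4 and 3 vs 6, together have about 8% probability with no treatment effect (8.2% at 15/15, 7.8% at 23/23), but only 0.4% at 15/43 and 1.0% at 20/40.
- An analyst with the SAP has the constants and both sample sizes and could derive 0.483. Whether that analyst would do so, or take the printed 0.5, cannot be known.
- SAP section 9 says the study was terminated early. The documents do not say whether the 39-patient look took place, so the practical value may now lie in reporting the interim rule correctly.

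**Conclusion.** The inconsistency is real. The interim cutoff implied by the plan's formula, by Table 9 and by Table 10 is 0.483; the written 0.5 contradicts all three. The likely cause is rounding to one decimal, although neither document says so and the final cutoff is given to two decimals.

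The effect is on early stopping. Applying 0.5 would add about 8 to 10 percentage points when the arms do not differ. It would add 1.5 to 4 points in the scenarios with a true difference, which is a relative increase of more than half in each (for example 7.14% to 11.10% at 20/40). Power falls by about 0.4 points and type I error is essentially unchanged. This should be corrected, but it does not threaten the primary conclusion.

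The figures assume exactly 13 control and 26 combination patients at the interim, as in Table 9, and that the interim rule is followed. The first 39 patients need not split exactly 13:26; with another split the formula cutoff is still 0.483, but the boundaries and stopping rates would differ.

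**What to change.** In Protocol 9.2 and SAP section 8, replace the interim 0.5 with 0.483 and show its derivation, 0.96 × (39/81)^0.94. Reproduce Table 9 in SAP section 8 and state that the formula and this table govern. This costs one number in each document and one copied table, and it leaves Tables 9 and 10 as they are.

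A protocol change to the study design needs ethics approval under Protocol 10.2. With the study terminating early, a clarification in the SAP and the study report naming the formula and Table 9 as the governing rule would serve the purpose. If the interim look has already taken place, the report should state which cutoff was applied and whether the result fell in one of the five conflicting outcomes.

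If 0.5 was intended, the interim boundaries in Table 9 for 2 to 6 control responders each rise by one, λ(n/N)^α no longer describes the interim rule, and Table 10 must be rerun.
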